The duration of standard local anesthetic formulations vary from 4-8 hours and administration can include single injections or continuous infusion catheters. Liposomal bupivacaine, Exparel®, has a prolonged duration of action of up to 96 hours. Studies have verified its safety with a very low risk of dysrhythmias, local tissue reaction, effects on wound healing or nerve toxicity. In the elective surgical setting, liposomal bupivacaine has been shown to have an opioid sparing effect, increased duration of analgesia, increased patient satisfaction, earlier discharge, and lower hospital cost. This formulation has not been studied in trauma patients and its novel use may impact practice in pain management of trauma patients. Patients may exhibit a lower opioid requirement with the use of the liposomal bupivacaine. In addition, this may reduce the incidence of untoward effects including respiratory depression, central nervous system depression, and gastrointestinal dysfunction, and subsequently speed recovery with improved mobilization and cooperation with physical therapy. To date, no studies have evaluated liposomal bupivacaine regional analgesia following extremity trauma. This pilot study aims to assess the

efficacy of long-acting liposomal bupivacaine compared to ropivacaine 0.2% in orthopedic trauma patients with acute pain following femur or hip fracture.

6) Inclusion and Exclusion Criteria

Inclusion criteria:

- 1) age \geq 18 years \leq 70 years
- 2) Patient's s/p trauma, with confirmed femur and/or hip fractures with a planned admission to the hospital.
- 3) Patient is ambulatory without assistance (e.g. walker, cane, caretaker) prior to incident.

Exclusion Criteria:

- 1) >10 hours since presentation to the emergency department
- 2) History of seizure disorder, recent seizure or a document intra-cranial hemorrhage.
- 3) Central or peripheral neurologic deficit on presentation
- 4) Concern or compartment syndrome
- 5) Associated additional long bone fractures
- 6) End stage liver failure
- 7) Renal failure requiring dialysis
- 8) Pregnancy or breast feeding
- 9) Prisoners
- 10) Coagulopathy with INR >1.5
- 11) Use of direct thrombin inhibitors (bivalirudin, argatroban, desirudin, dabigatran etexilate), or direct factor Xa inhibitors (rivaroxaban, apixaban, edoxaban)
- 12) Suspected prolonged intubation within first 12 hours secondary to respiratory failure other than peri-procedurally
- 13) Adults unable to consent

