- 14) Pediatric patients <18 years old
- 15) Patients exhibiting signs of shock upon admission, HR >120 or SBP <100 mmHg.
- 16) History of allergic reaction to local anesthetics
- 17) Administration of any other local anesthetic in the 2 hours prior to the study enrollment.
- 18) Distal femur fractures

7) Number of Subjects

17 patients per arm

Total subjects: 34

8) Recruitment Methods

Subjects will be recruited from the UC Davis Trauma Center. Patients found to have femur and /or hip fractures admitted to UCDMC will be screened for eligibility.

Waiver of HIPAA authorization for recruitment is requested for access to PHI during the screening to determine eligibility.

Description of PHI that will be accessed.

Information reviewed to assess eligibility will include: date of admission, date of birth, gender, mechanism of trauma injury (blunt/penetrating), x-rays, lab results, admission vital signs, home medications and the patient's medical history.

The use of PHI involves no more than minimal risk and granting of waiver will not adversely affect privacy of the patients.

Access to medical records that contain patient's personal information for the purpose of this study will be limited to the approved research personnel. These personnel already have knowledge of and access to identifiable medical information of current trauma patients as part of their daily job functions; hence, granting of this waiver will not adversely affect the privacy of the involved patients or the confidentiality of their information. EMR access to PHI is password-protected and no PHI will be reused or disclosed to any

other person or entity, except as required by law. Data will be used solely for the purposes of determining study eligibility.

The research could not practicably be conducted without a waiver or alteration.

Without an initial review of the medical record for screening purposes, it would not be possible to identify potential subjects and confirm their applicability for study participation.

The research could not practicably be conducted without access to and use of PHI.

Since PHI is embedded in the medical record and since the screening process requires detailed information about trauma patients, access to medical records (viewing of PHI) is necessary.

9) Compensation to the Subjects

Subjects will not be compensated for this study.

10) Study Timelines

The duration of each subject's participation is the length of their hospital stay.

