For patients randomized to receive ropivacaine, IP will be prepared via straight draw of ropivacaine 0.2% (120mg) and equally divided into three syringes. For patients randomized to receive liposomal bupivacaine (266mg), a dilution will be prepared, using 20mL of liposomal bupivacaine (Exparel®) 1.3% (13.3mg/mL) and 40mL of 0.9% NaCl. While the stability of ropivacaine drawn into a syringe is longer than 4 hours at room temperature, in order to maintain the blind, all IP will be given a stability of 4 hours at room temperature.

The three syringes will be dispensed in a tamper-proof opaque bag and will be transported between the Pharmacy and Emergency Department by either a Pharmacy member or CRC. The tamper-proof opaque bag will contain a note of "CAUTION," that the content of the bag contain unblinding information.

The unblinded administering ED Physician will receive the IP and confirm that the opaque bag has not been tampered with. Prior to breaking the seal for drug administration, the unblinded ED Physician will ensure that the blinded primary nurse has transferred care to the unblinded procedure nurse, and that all blinded members of the healthcare team have left the exam room.

An unblinded Emergency Department staff will perform an ultrasound-guided fascia iliaca compartment block (FICB) per the institutional ER protocol, using 60mL of either ropivacaine 0.2% (266mg) or a diluted solution of liposomal bupivacaine (266mg).

The patient will be placed on a continuous pulse oximetry and telemetry monitoring. Using standard sterile technique, a dermal wheel will be created using 0.25% bupivacaine. Under ultrasound guidance, a blunt tipped needle will be inserted under the fascia iliaca muscle just inferior to the inguinal ligament and lateral to the neuro-vascular bundle. After a negative aspiration, the designated local anesthetic will be infused slowly over several minutes in 5 ml increments with aspiration between to the 5 ml increments to confirm extravascular insertion. The volume and dosing will be as listed above.

Immediately following the procedure, to prevent unblinding of blinded personnel, the syringes will be discarded per standard institutional procedures into opaque Sharps containers. Upon completion, the patient will remain on telemetry monitoring for 4 hours.

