The patient will be blinded and all members of the healthcare team will be blinded from the point of transfer of care from the Emergency Department physicians to the receiving service.

Both groups will be able to receive as needed analgesia per the primary attending service. (e.g., oral hydrocodone/acetaminophen 5/325 mg or narcotic IV push as needed for breakthrough pain).

Patients enrolled in the study will be given a light blue wristband for identification to alert physicians regarding restrictions for anesthetics. Additionally, an automatic alert notification will be given by the Electronic

Medical Record system if additional local anesthetics are ordered for the patient.

Pain Assessment

Objective pain assessment will be evaluated by the UCDMC nursing staff per local standard of care which is every four hours while the patient is awake using a numeric rating scale (NRS) of 0 to 10 with a pain score of 0 being defined as: no pain, 1-4 mild pain, 5-7 defined as moderate pain, and 8-10 defined as severe pain.

Study Definitions

Acute and hospital-related adverse effects and study outcomes will be collected and tracked prospectively during the FICB and throughout the hospital stay, as appropriate per endpoint.

During hospital stay study outcomes

Data collection will include total amount of opioids administered to study patients in morphine equivalents (see Appendix) and the use of other analgesic medications during this time period. Adjunctive analgesic use including non-steroidal anti-inflammatory drugs, acetaminophen, and gabapentin will be quantified. Use of additional adjunctive agents such as muscle relaxants also will be collected.

All objective pain and agitation scores reported by the NRS will be collected; duration of supplemental oxygen requirement; number of episodes of oxygen desaturation (arterial O₂ sat below 92%); morning incentive spirometer and peak flow measurements; 24-hour antiemetic (e.g., promethazine; ondansetron) pharmacotherapy; time to first bowel movement; and need for anti-hallucination or anti-delirium pharmacotherapy.

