15) Provisions to Monitor the Data to Ensure the Safety of Subjects

This study involves minimal risk to the patient, however, the DoD requires an independent research monitor for all clinical studies and thus a medical monitor will be assigned. [name], MD, Professor of Surgery and Vice Chair of Surgery will act as the Data Safety Monitor for this study. Any unanticipated adverse event meeting grade 3 or grade 4 as listed below per the FDA's guidance for industry, will be reported to the study medical monitor. The medical monitor will keep a database of the reported events and will report any of the above adverse events to the FDA's MedWatch. In addition, subjects having experience an adverse

event of Grade 3 or 4 will be followed by the PI for the duration of their hospitalization.

The greatest risk for systemic toxicity is at the time of administration and most often as a result of inadvertent intravenous injection of the drug with rapid onset of symptoms. The procedure will be performed per UCDMC's "Hip Fracture Protocol" which includes routine fascia iliaca compartment blocks, a provider training protocol and routine ultrasound guidance. The protocol also includes telemetry monitoring, continuous pulse oximetry and q 15 min neurologic assessments for 30 min following injection. In addition, the patients will remain on telemetry for an additional 4 hours monitoring for any delayed events.

Following this 4 hour period, evaluation and capture of adverse events will continue until the completion of the 96 hour study period. This will consist of nursing evaluation and vitals every 4 hours around the clock and on an as needed basis. The study coordinator will evaluate for any potential events on a daily basis throughout the study period. The PI or co-PI will be notified directly of any severe adverse event at the time of the event.

The definitions of an adverse event are in line with the WHO-UMC system for standardized case causality assessment.

Causality term	Assessment criteria*
Certain	
• Event or laboratory test abnormality, with plausible time relationship to drug intake• Cannot be explained by disease or other drugs• Response to withdrawal plausible (pharmacologically, pathologically)• Event definitive pharmacologically or phenomenologically (i.e. an objective and specific medical disorder or a recognised pharmacological phenomenon)• Rechallenge satisfactory, if necessary

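### Exclusion 17's 2-hour window is shorter than the protocol's own 4-8 hour local-anesthetic duration, so the full 60 mL study block can be given over an earlier block still within its stated duration

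*Combined protocol and SAP*

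**What the plan says.** All references are to the combined protocol and SAP.

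- **Section 6, Exclusion 17** bars "Administration of any other local anesthetic in the 2 hours prior to the study enrollment". No reason is given for the 2-hour figure.
- **Section 5 (Background)** states: "The duration of standard local anesthetic formulations vary from 4-8 hours and administration can include single injections or continuous infusion catheters". Of liposomal bupivacaine it says that it "has a prolonged duration of action of up to 96 hours".
- **Section 6, Exclusion 1** removes patients with ">10 hours since presentation to the emergency department", so enrollment can take place at any time up to hour 10.
- **Section 6, Exclusion 3** removes patients with "Central or peripheral neurologic deficit on presentation".
- **Section 12 (Procedures Involved)** fixes the study block at 60 mL in both arms. It gives no reduction for earlier local anesthetic. On prepared syringes it says that "all IP will be given a stability of 4 hours at room temperature".
- **Section 12** also provides that "Patients enrolled in the study will be given a light blue wristband for identification to alert physicians regarding restrictions for anesthetics", and adds an automatic record alert for further local-anesthetic orders.
- **Section 15** describes the hospital's hip fracture protocol as one "which includes routine fascia iliaca compartment blocks".

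**The concern.** Exclusion 17, the wristband and the record alert all point the same way: the plan does not want local anesthetics stacked. Yet the look-back is half the shortest duration that the protocol itself cites. The patient who slips through is one blocked in the ED after arrival and enrolled more than 2 hours later.

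No other provision shown catches this patient:

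- Exclusion 3 looks at deficits on arrival, so it cannot detect a block placed afterwards.
- The wristband and alert act on enrolled patients and new orders, not on doses already given.
- The text has no cumulative dose limit and no check for a residual block.

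What is at stake is patient safety. Section 17 (Risks to Subjects) attributes severe reactions mainly to toxic systemic concentrations, and an earlier block adds to the total amount of drug given. Section 5 says that the liposomal product has not been studied in trauma patients, which is a reason to avoid exposure that is easy to avoid.

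**Working it through.** **Inputs from the documents.** Look-back 2 h before enrollment (Exclusion 17). Duration D of standard agents 4-8 h (section 5). Latest enrollment at hour 10 (Exclusion 1). Study block 60 mL (section 12).

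**Assumption.** The lag L from enrollment to injection is not stated. I take 0-4 h. The upper end borrows the 4-hour syringe limit in section 12, which strictly runs from preparation, not from enrollment.

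**Dose check.** 60 mL × 2 mg/mL = 120 mg ropivacaine; 20 mL × 13.3 mg/mL = 266 mg liposomal bupivacaine. Both agree with the doses in section 30.

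**Stated duration left at the study injection**, for an earlier block placed just over 2 h before enrollment: max(0, D − 2 − L).

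| Lag L | D = 4 h | D = 6 h | D = 8 h |
|---|---|---|---|
| 0 h | 2 h | 4 h | 6 h |
| 2 h | 0 h | 2 h | 4 h |
| 4 h | 0 h | 0 h | 2 h |

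The lag narrows the overlap. For a 4 h agent it is gone once the lag reaches 2 h; for an 8 h agent 2 h still remain after a 4 h lag.

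**Worked case.** Block at hour 3, enrollment at hour 6. Elapsed time is 3 h, which exceeds 2 h, and hour 6 is within 10 h, so Exclusions 17 and 1 both pass the patient. Stated duration left at enrollment: 4 − 3 = 1 h to 8 − 3 = 5 h.

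**Where the cut-off falls for enrollment at hour 10.** The current rule passes any ED block placed before hour 10 − 2 = 8. A look-back of 8 h to injection passes it only if placed by hour 10 − 8 = 2 (injection at once) or by hour 10 + 4 − 8 = 6 (injection 4 h later).

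**Effect of a longer look-back to injection.** 8 h leaves 8 − 8 = 0 h at every stated duration. 4 h would still leave up to 8 − 4 = 4 h.

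**Amount of drug, for scale only.** If the earlier block were 30-60 mL of 0.2% ropivacaine (an assumed range), it would add 60-120 mg given. That is not the amount still circulating.

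**Primary endpoint.** An earlier block can lengthen coverage in the ropivacaine arm only if it outlasts the study block. The extreme is an 8 h earlier block with 6 h left and a study block lasting 4 h: 6 − 4 = 2 h, or 2/96 = 2.1% of the 96 hours. If both blocks last equally long, the gain is zero.

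**The case against.** The strongest reply is that 4-8 hours describes how long a formulation works, not how long drug stays in plasma, so it is no toxicity washout. Sections 15 and 17 place the greatest systemic risk at the moment of administration, mostly from accidental intravenous injection. Section 30 notes that ropivacaine is approved for continuous infusion, so ongoing exposure to that drug is not in itself treated as hazardous. And section 12 gives every patient a bupivacaine skin wheal anyway.

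The scenario may also be rare. ED staff perform the study block under the institutional protocol, so it may usually replace the routine block.

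Most of this stands, and it limits the point. It does not close the gap: nothing in the criteria requires the study block to be the first block, and the protocol offers no other basis for 2 hours.

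A reader might infer more than the documents support:

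- *The combined dose is toxic.* No maximum dose or plasma level is given, so this cannot be shown.
- *Counting back from enrollment rather than injection makes the overlap worse.* The table shows the reverse.
- *Causality grading would be compromised.* An earlier block is another possible cause, but a reaction soon after a fresh 60 mL injection, in a patient who had tolerated the first block for over 2 hours, points in time to the study drug. Reporting to the monitor in section 15 depends on grade and on the event being unanticipated, not on the causality category.
- *A given share of patients is affected.* The documents give no data on when or how often earlier blocks are placed.

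**Conclusion.** The point holds as a gap in eligibility, of modest weight. On the protocol's own figures, a patient can receive the full study block with up to 2-6 h of an earlier block's stated duration left if injected at once, or 0-2 h after a 4 h lag. The lag is an assumption. The 4-8 h range is the protocol's own, read as duration of effect.

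The consequence is avoidable cumulative exposure of unknown frequency and undemonstrated harm. It is not a threat to the primary analysis: 2.1% of the 96-hour period at the extreme is negligible. The case for acting is that the plan already aims to prevent stacking and the correction is cheap.

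**What to change.** Keep the 2-hour rule for minor infiltration and add to Exclusion 17: *or a single-injection regional block of the fractured limb within 8 hours before the planned study injection, or any liposomal local anesthetic for this injury.*

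Eight hours is the upper end of the range in section 5 and leaves no stated duration at injection. It is a choice taken from that range, not from a safety threshold. Liposomal drug is named separately because, at up to 96 h, 8 hours does not cover it. Earlier liposomal use in these patients may be rare, but naming it costs nothing. A running catheter needs no separate clause, since infusion within 2 hours of enrollment is already barred.

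The cost is one clause and the loss or delay of some recently blocked patients from a target of 34 in 12 months. Their number is unknown, as is the frequency of the problem, but both should be small if the study block usually replaces the routine one. Screening before the routine block limits the loss, and patients more than 8 hours past an earlier single-injection block remain eligible. A patient blocked at hour 3, for example, could be enrolled by hour 10 and injected from hour 11 (3 + 8).

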Achieving adequate pain control in trauma patients proves challenging. Consequences of uncontrolled pain include immobility, respiratory compromise, exhaustion due to lack of sleep, disorientation, agitation, stress response, and post-traumatic stress disorder. The standard of care for analgesia in poly-trauma patients is the use of opioids administered via intravenous, epidural, or enteral routes with either intermittent dosing or as patient-controlled analgesia. Though opioid agents can provide effective analgesia, they exhibit untoward effects that at times may be dose limiting. These adverse effects include hypotension, bradycardia, central nervous system depression, respiratory depression, somnolence, and nausea. Additional common side effects of opioid use include pruritus, dry mouth, urinary retention, vomiting, prolonged recovery of ileus, and constipation. Clinicians are becoming increasingly aware of additional consequences, such as, opioid tolerance necessitating increased doses, opioid induced hyperalgesia, and opioid dependence. As such, increasing emphasis has been placed on a multimodal approach to the management of postoperative and post-traumatic pain. This multimodal approach includes use of local and regional blocks using local anesthetics.

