Duration anticipated to enroll all study subjects: 12 months.

Data acquisition and analysis: same 12 months

Manuscript preparation: 6 months

Total time requirement: 1.5 years

11) Study Endpoints

Hypothesis: In patients with femur or hip fractures, a fascia iliaca compartment block using liposomal bupivacaine will require less total opioid administration compared to a fascia iliaca block using 0.2% ropivacaine.

Primary Endpoint

(1) Total opioid requirement during the 96 hour randomization period measured in milligram morphine equivalents.

Secondary Endpoint

(1) Percentage of time during the 96 hour randomization period that the objective pain score was above mild (defined as a numeric rating score >4).

12) Procedures Involved

The nature of the risks and benefits associated with participation in the study will be explained to all potential study subjects. Written informed consent must be obtained before the subject can begin any screening procedures that are not considered standard patient care. Subjects who have undergone the screening procedures and have met the entry criteria will be randomized into the study and assigned to treatment by the Unblinded Pharmacist. Subjects will be randomized in a computer-generated, blinded block, 1:1 ratio to treatment with 60mL of either 0.2% ropivacaine (120mg) or a dilution of liposomal bupivacaine (266mg).

The Pharmacy and Emergency Medicine (EM) members will be the only unblinded study team members. All other members, including the Trauma team and Clinical Research Coordinator (CRC), will remain blinded.

The unblinded Investigational Drug Service (IDS) Pharmacy at UC Davis Health (UCDH) will be responsible for blinding and drug preparation. Investigational Product (IP) will be prepared in three 35mL Luer lok syringes, each containing 20mL of IP, for a total dose of 60mL. In addition to a patient-specific institutional label, masking/amber tape will also be affixed to the syringes in order to reduce the risk of drug recognition by a supporting procedure nurse. During the procedure, nursing care of the patient will temporarily transition from the primary bedside nurse to a supporting procedure nurse. The supporting procedure nurse will remain blinded and will assist primarily with assessments and recording of vital signs (but will not work directly with the IP).

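### The secondary endpoint is a percentage of the 96-hour period, but pain is scored only in waking hours, and no rule says how unscored time enters the percentage.

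*Combined protocol and SAP*

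**What the plan says.** Section 11 lists one secondary endpoint: "Percentage of time during the 96 hour randomization period that the objective pain score was above mild (defined as a numeric rating score >4"). The cut-off agrees with the pain categories in Section 12, where 1 to 4 is mild.

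Under Pain Assessment in Section 12, nursing staff score pain "every four hours while the patient is awake using a numeric rating scale (NRS) of 0 to 10". Section 12 also says that all recorded scores will be collected.

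Section 15 describes continued safety surveillance after the first four hours: "This will consist of nursing evaluation and vitals every 4 hours around the clock and on an as needed basis". Its stated purpose is to capture adverse events, and it does not mention the pain scale.

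The Statistical Analysis text in Section 14 assigns chi-square or Fisher's exact tests to the secondary endpoint and plans to present it with interquartile ranges. It gives no rule for turning spot scores into time, for sleep or sedation, for missed scores, or for patients who leave before 96 hours. Section 10 ends participation at hospital discharge, so early leavers are possible.

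**The concern.** The endpoint covers hours for which the plan schedules no score. Some rule must fill them, and different rules give different answers from the same data. If the choice is left to the analysis stage, the result depends on a decision that was not fixed in advance.

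The most literal rule keeps all 96 hours in the denominator and counts only time with a recorded score above 4. Each patient's result is then waking pain multiplied by the fraction of the 96 hours spent awake and scored. That fraction may depend on treatment. Section 5 says of opioids: "These adverse effects include hypotension, bradycardia, central nervous system depression, respiratory depression, somnolence, and nausea". Section 12 lets opioid exposure differ between arms, since "Both groups will be able to receive as needed analgesia per the primary attending service". Section 11 expects it to differ, in that "a fascia iliaca compartment block using liposomal bupivacaine will require less total opioid administration compared to a fascia iliaca block using 0.2% ropivacaine". A difference in scored time could therefore pass for a difference in pain, or hide one.

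The trial is a pilot meant to inform larger trials (Section 4), so an ambiguous pain measure could be carried into them.

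**Working it through.** The plan states no figure for this endpoint, so there is none to reproduce.

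**Inputs from the document:** a 96-hour period and a threshold above 4 (Section 11); scoring at four-hour intervals in waking hours (Section 12).

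**Assumed inputs (the document gives none):** sleep or sedation of 8, 10 or 12 hours per day; 30% to 70% of waking assessments above 4; each scored assessment stands for four waking hours.

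**Scored assessments.** At most 96/4 = 24 per patient.
- 8 h sleep per day: 4 × 16 = 64 waking hours, 64/4 = 16 assessments.
- 10 h: 4 × 14 = 56 waking hours, 14 assessments.
- 12 h: 4 × 12 = 48 waking hours, 12 assessments.

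**Literal 96-hour denominator.** With p the share of waking assessments above 4 and s the hours of sleep per day, the endpoint is p × (24 − s)/24.

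*Dilution with equal sleep (8 h in both arms).* 0.40 × 16/24 = 26.7% and 0.50 × 16/24 = 33.3%. The true 10-point gap becomes 6.7 points.

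*False difference with equal waking pain (p = 0.50).*
- 8 versus 10 h: 8/24 = 33.3% versus 7/24 = 29.2%, a gap of 4.2 points.
- 8 versus 12 h: 33.3% versus 6/24 = 25.0%, a gap of 8.3 points.
- Over p = 0.30 to 0.70, the gap is 2.5 to 5.8 points (8 versus 10 h) and 5.0 to 11.7 points (8 versus 12 h).
- With equal sleep, the gap is 0.

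*Both together (waking pain 40% liposomal bupivacaine, 50% ropivacaine).*

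| Sleep, liposomal / ropivacaine | Liposomal | Ropivacaine | Gap (ropivacaine minus liposomal) |
|---|---|---|---|
| 8 h / 8 h | 26.7% | 33.3% | 6.7 |
| 8 h / 10 h | 26.7% | 29.2% | 2.5 |
| 8 h / 12 h | 26.7% | 25.0% | −1.7 |
| 10 h / 8 h | 0.40 × 14/24 = 23.3% | 33.3% | 10.0 |
| 12 h / 8 h | 0.40 × 12/24 = 20.0% | 33.3% | 13.3 |

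A 10-point waking benefit can thus reverse or be exaggerated, depending on which arm sleeps more.

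**Last score carried forward.** Take one patient with p = 0.50 and 8 h sleep: 32 of 64 waking hours are above 4, and 32 hours are asleep. If every score before sleep is 4 or less, the result is 32/96 = 33.3%. If every one is above 4, it is (32 + 32)/96 = 66.7%.

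**Scored assessments as denominator.** The same patient has 8/16 = 50%. Between arms, 40% versus 50% stays 40% versus 50% whatever the sleep pattern, as long as waking pain itself is unaffected.

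**The case against.** The strongest reply is that the plan never says unscored time counts as time without pain. The reference to 96 hours can be read as the observation window, with scored time as the denominator, and the sleep artefact calculated above then disappears. Carry-forward is also possible, and it can place sleeping hours in the numerator. This stands: the literal denominator is one permitted reading, not a stated rule. The defect is the missing rule.

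A reader might infer something stronger: that the endpoint is biased against liposomal bupivacaine, because the arm with more opioid would be sleepier and scored less. The documents do not support that.
- Section 5 does list somnolence as an opioid effect, but it also names sleep loss as a consequence of poorly controlled pain, which points the other way.
- Section 17 lists both insomnia and somnolence among the common reactions to liposomal bupivacaine.
- No figures on sleep or sedation are given for either arm.

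A 4-hour daily gap in sleep sustained over four days is also a large assumption. At 2 hours the false difference is about half as big, and at equal sleep it is zero.

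A further objection is that restricting to scored assessments conditions on being awake, which treatment may affect. If pain keeps patients awake, painful time is over-represented. This also stands, and it is why a sensitivity analysis is needed.

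Finally, the point touches a secondary endpoint in a 34-patient pilot. The primary endpoint, total opioid use, is unaffected.

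**Conclusion.** The concern holds as a gap in definition. The secondary endpoint spans 96 hours, scores are planned only for waking time, and no rule covers the rest. The safety checks in Section 15 do not fill the gap.

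If the 96 hours is used literally, the endpoint mixes pain with time awake. Equal sleep of 8 hours per day removes a third of any true difference. Unequal sleep creates a false one of about 4 points (8 versus 10 hours) or 8 points (8 versus 12 hours) at 50% waking pain. These sizes rest wholly on assumed sleep and pain levels. The direction of any net bias is not established.

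This should be corrected before analysis, because the unstated rule can change the size and even the sign of the result.

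**What to change.** In Section 11, define the endpoint as each patient's percentage of scored (awake) assessments with a score above 4, within 96 hours or until discharge if earlier. State that missed assessments and time asleep or sedated are left out of both numerator and denominator.

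In the Statistical Analysis text, compare the per-patient percentages between arms with a Wilcoxon rank sum test, which the plan already names for the primary endpoint. Chi-square and Fisher's exact tests compare counts in categories and do not suit one percentage per patient. Present medians with interquartile ranges.

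Report the number of scored assessments per patient by arm, so that a difference in scored time is visible. Add one prespecified sensitivity analysis under another rule for unscored time, such as the 96-hour denominator or the last score carried forward.

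Cost: no added data collection, since all recorded scores are already to be collected. It is more than a wording change, however: the test changes, and the endpoint then describes waking pain among assessments that treatment may influence. The sensitivity analysis shows how far the conclusion depends on that choice.
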